5. STUDY TREATMENT

5.1. Treatment Dosage and Administration

The specific study drugs, formulation, dosage, administration, and schedule are detailed in Tables 1 and 2 and the sections that follow. Study treatment will be administered on an outpatient basis. Each treatment cycle will be 4 weeks (28 days in duration).

The commercial product for each study drug will be supplied for this trial. Vemurafenib will be provided by Genentech, and Sofarafenib will be provided by Bayer. Refer to Section 9 for Drug Treatment Information and link to prescribing information (package inserts).

Table 1: Study Drugs

Agent	Formulation	Dose	Route	Schedule	Cycle Length
Vemurafenib	240 mg tablets	480 mg	PO	BID	28 days
Sorafenib	200 mg tablets	200 mg	PO	BID	28 days

Table 2: Study Drug Dose Levels

	Vemurafenib	Sorafenib
Dose level 1 (starting dose)	480 mg PO BID	200 mg po bid
Dose level -1	240 mg PO BID	200 mg daily

5.2. Administration of Vemurafenib + Sorafenib

Patients will be asked to take the specified number of tablets for their prescribed dose on an empty stomach at a regular time each day with water. Doses should be taken either one hour prior or two hours after a meal. Approximately 12 hours should elapse between doses.

5.3. Toxicities and Dosing Delays / Dose Modifications

Any patient who receives study treatment on this trial will be evaluable for toxicity. Each patient will be assessed for the development of toxicity according to the Schedule of Events (Appendix A). Toxicity will be graded according to the NCI CTCAE, Version 5 which is available at:

https://ctep.cancer.gov/protocoldevelopment/electronic_applications/docs/CTCAE_v5_Quick_Reference_5x7.pdf

For any dose interruptions, re-initiation of study treatment may be delayed for a maximum of 28 days to allow recovery from any toxicity. In exceptional cases where subjects are responding, re-initiation of therapy after missing > 28 consecutive days of treatment may be considered on a case-by-case basis after confirmation with the Principal Investigator.

Treatment related toxicities will be attributed by investigators, and causality will be assessed individually for each of the study drugs in the combination regimen, both Vemurafenib and Sorafenib (Refer to Section 8.4).

Dose modifications and treatment delays based on observed drug-related toxicity will be performed as described in Sections 5.3.1. and 5.3.2 and will follow the prescribing information:

Vemurafenib

(https://www.accessdata.fda.gov/drugsatfda_docs/label/2020/202429s019lbl.pdf)

Sorafenib

(https://www.accessdata.fda.gov/drugsatfda_docs/label/2018/021923s020lbl.pdf)

In the event that either Vemurafenib or Sorafenib is to be discontinued due to toxicity, both drugs are to be discontinued and the patient is to have off treatment procedures completed (Section 6.3). The patient is to be followed for 30 days after withdrawal from study treatment for adverse events (Section 6.4), and every 3 months until study completion for survival status.

5.3.1. Vemurafenib and Sorafenib Dose Modifications

Vemurafenib and sorafenib should be withheld for Grade 3 or greater adverse reactions due to study treatment. Upon recovery to Grade 0-1, restart vemurafenib and sorafenib at a reduced dose (dose level -1) as follows:

- Vemurafenib 240 mg twice daily plus sorafenib 200 mg daily for first appearance of Grade 3 or greater adverse reactions.
- Stop therapy for second appearance of Grade 3 or greater

If dose reductions below Vemurafenib 240 mg twice daily or sorafenib 200 mg po daily are indicated, the patient will be withdrawn.

Vemurafenib should be discontinued for any of the following:

- Grade 4 adverse reaction, first appearance (if clinically appropriate) or second appearance
- QTc prolongation > 500ms and increased by > 60s from pre-treatment values.

Temporary interruption of sorafenib is recommended in patient undergoing major surgical procedures.

Table 3: Adverse Reactions Requiring Dose Modification of Sorafenib

Adverse Reaction	CTCAE Grade	Action	Dose reduce and resume sorafenib
Cardiovascular Events			
Cardiac ischemia and/or infarction	Grade 2 and above	Permanently discontinue	Do not resume
Congestive heart failure	Grade 3	Interrupt ^a until ≤ Grade 1	Decrease to 200mg daily
	Grade 4	Permanently discontinue	Do not resume
Hemorrhage requiring medical intervention	Grade 2 and above	Permanently discontinue	Do not resume
Hypertension	Grade 2 asymptomatic and diastolic pressure 90-99mmHg	Treat with anti-hypertensive therapy	Continue sorafenib dosing as scheduled and closely monitor blood pressure
	Grade 3	Interrupt until symptoms resolve and diastolic blood pressure < 90mmHg	Treat with anti-hypertensives. Decrease to 200 mg daily when resumed.

			If further reduction is needed patient is to be withdrawn.
	Grade 4	Permanently discontinue	Do not resume
Gastrointestinal Perforation	Any grade	Permanently discontinue	Do not resume
QT Prolongation	Monitor electrolytes and ECG. If QTc is >500ms or for an increase from baseline of 60ms or greater	Interrupt Correct electrolyte abnormalities (magnesium, potassium, calcium)	Use medical judgement before restarting
Severe DILI	≥ Grade 3 ALT in the absence of another cause ^c AST/ALT > 3xULN with bilirubin > 2x ULN in the absence of another cause ^c	Permanently discontinue	Do not resume
Non-hematological toxicities	Grade 2	Treat on time	Decrease to 200 mg daily
	Grade 3		
	1 st occurrence	Interrupt until ≤ Grade 2	Decrease to 200 mg daily

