1.3. Study Agent(s) Background and Associated Known Toxicities

1.3.1. Vemurafenib

Vemurafenib is a type I½ RAF inhibitor. Vemurafenib is also an orally available inhibitor of some mutated forms of BRAF serine-threonine kinase, including BRAF V600E. Vemurafenib inhibits other kinases in vitro such as; CRAF, ARAF, wild-type BRAF, SRMS, ACK1, MAP4K5, and FGR at similar concentrations. At steady state, Vemurafenib exhibits linear pharmacokinetic within the 240 mg to 960 mg dose range.

There has been a tremendous amount of clinical experience with Vemurafenib. The most common adverse events include (≥30%): arthralgias, rash, alopecia, fatigue, photosensitivity reactions, nausea, pruritus and skin papillomas. Special precautions from the package insert include new primary cutaneous malignancies, new non-cutaneous squamous cell carcinomas, tumor promotion in BRAF wild-type melanoma patients, serious hypersensitivity reactions (anaphylaxis and Drug Reaction with Eosinophilia and Systemic Symptoms - DRESS syndrome), Stevens-Johnson syndrome and toxic epidermal necrolysis, QT prolongation, hepatotoxicity, photosensitivity (advise patients to avoid sun exposure), uveitis, harm to the fetus, radiation sensitization and recall, and

renal failure. Vemurafenib is currently approved for patients with BRAF V600E mutated melanoma as well as for patients with BRAF V600E mutated Erdheim-Chester disease.

1.3.2. **Sorafenib**

Sorafenib is a kinase inhibitor that inhibits multiple intracellular (CRAF, BRAF and mutant BRAF) and many surface kinases (KIT, FLT3, RET, RET/PTC, VEGFR-1, VEGFR-2, VEGFR-3 and PDGFR- β). It is currently FDA approved for the treatment of patients with hepatocellular carcinoma, advanced renal cell carcinoma and locally recurrent or metastatic, progressive differentiated thyroid carcinoma refractory to radioactive iodine treatment. Sorafenib is a type II BRAF kinase inhibitor (traps their target kinases in an inactive so-called DFG-out state occupying a hydrophobic pocket adjacent to the ATP binding site (Kufareva and Abagyan 2008). The agent has had very extensive clinical trials. No trials with Sorafenib as a single agent in patients with advanced pancreatic cancer have been reported. However, Sorafenib has been added to a gemcitabine+cisplatin combination in patients with advanced pancreatic cancer with no indication for improving the response rate or median progression free survival over what was achieved with chemotherapy alone.

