 - d. Unstable angina (anginal symptoms at rest), new-onset angina within 3 months before randomization, or myocardial infarction within 6 months before randomization.
9. Has history of (non-infectious) pneumonitis that required steroids or current pneumonitis.
10. Has an active infection requiring systemic therapy.
11. Evidence or history of bleeding diathesis or coagulopathy
12. Patient with any pulmonary hemorrhage/bleeding event of NCI-CTCAE v5.0 ≥ Grade 2 within 4 weeks before initiating study treatment; any other hemorrhage/bleeding event of NCI-CTCAE v5.0 ≥ Grade 3 within 4 weeks before initiating study treatment.
13. Patient with thrombotic, embolic, venous, or arterial events, such as cerebrovascular accident (including transient ischemic attacks) within 6 months of informed consent.
14. Presence of a non-healing wound, non-healing ulcer, or bone fracture.
15. History of organ allograft (including corneal transplant).
16. Known or suspected allergy or hypersensitivity to any of the study drugs (sorafenib, and or vemurafenib) study drug classes, or excipients of the formulations given during the course of this trial.
17. All patients with known diagnosis of Neurofibromatosis Type 1 or other known RAS-opathies
18. Patients with uncontrolled seizures
19. Treatment with medications that have known risk of QTc interval prolongation or Torsades de Pointe (TdP) within 14 days or 5 half-lives before dose of either drug is given in this study and for the duration of the study. Refer to Appendix E1 for medications with a known risk of TdP.

20. Treatment with a strong or moderate CYP3A inducers (e.g, phenytoin, carbamazepine, phenobarbital, St. John's Wort [*hypericum perforatum*], dexamethasone at a dose of greater than 16 mg daily, or rifampin [rifampicin], and/or rifabutin) or inhibitors within 28 days before dose of either drug is given in this study and for the duration of the study. Refer to Appendix G.
21. Malabsorption or other significant bowel or stomach resections
22. Has a history or current evidence of any condition, therapy, or laboratory abnormality that might confound the results of the trial, interfere with the patient's participation for the full duration of the trial, or is not in the best interest of the patient to participate, in the opinion of the treating investigator.
23. Has known psychiatric or substance abuse disorders that would interfere with cooperation with the requirements of the trial.

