9. DRUG / TREATMENT INFORMATION

9.1. Vemurafenib

Package Insert:

https://www.accessdata.fda.gov/drugsatfda_docs/label/2020/202429s019bl.pdf

Other names for the drug:

- Zelboraf®;
- propane-1-sufonic acid {3-[5-(4-chlorophenyl)-1H-pyrrolo[2,3-b]pyridine-3-carbonyl]-2,4-difluoro-phenyl}-amide
- C₂₃H₁₈ClF₂N₃O₃S molecular weight 489.9.

Classification - type of agent: A kinase inhibitor

Mode of action: Vemurafenib is a low molecular weight, orally available, inhibitor of some mutated forms of BRAF serine-threonine kinase, including BRAF V600E. Vemurafenib also inhibits other kinases in vitro such as CRAF, ARAF, wild-type BRAF, SRMS, ACK1, MAP4K5 and FGR at similar concentrations. Some mutations in the BRAF gene including V600E result in constitutively activated BRAF proteins, which can cause cell proliferation in the absence of growth factors that would normally be required for proliferation. Vemurafenib has anti-tumor effects in cellular and animal models of melanomas with mutated BRAF V600E.

Storage and stability: Vemurafenib tablets are to be stored in their original container with lids tightly closed at room temperature 20°C-25 °C (68 °F-77 °F). Storage temperature excursions are permitted between 15°C-30 °C (59°F-86 °F).

Protocol dose: 480 mg PO (2 x 240mg tablets) BID

Preparation: No preparation required.

Route of administration for this study: Oral

Availability: Provided by Genentech free of charge.

Patient Counseling Information:

- Advise the patient to read the FDA-approved patient labeling (Medication Guide) before starting vemurafenib.
- Advise the patient to avoid consuming grapefruit and grapefruit juice while take vemurafenib during study treatment as this may raise the levels of vemurafenib and could make side effects worse.
- Advise the patient to avoid the use of St. John's Wort while taking vemurafenib during study treatment as this may lower the levels of the drug, which can make it less effective.
- Vemurafenib increases the risk of developing new primary cutaneous malignancies. Patients should be advised of the importance of contacting their healthcare provider immediately for any changes in their skin.
- Anaphylaxis and other serious hypersensitivity reactions can occur during treatment and upon re-initiation of treatment with vemurafenib. Patients should be advised to stop taking vemurafenib and to seek immediate medical attention for symptoms of anaphylaxis and hypersensitivity.

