- Severe dermatological reactions can occur in patients receiving vemurafenib. Patients should be advised to stop taking vemurafenib and to contact their health-care provider for severe dermatologic reactions.
- Vemurafenib can prolong QT interval, which may result in ventricular arrhythmias. Patients should be advised of the importance of monitoring their electrolytes and the electrical activity of the heart (via and ECG) during treatment with vemurafenib.
- Liver injury leading to functional hepatic impairment, including coagulopathy or other organ dysfunction, can occur with vemurafenib. Patients should be advised of the importance of laboratory monitoring of their liver during treatment with vemurafenib and to contact their health-care provider for relevant symptoms.
- Vemurafenib can cause mild to severe photosensitivity. Patients should be advised to avoid sun exposure, wear protective clothing, use a broad-spectrum UVA/UVB sunscreen and lip balm (SPF≥30) when outdoors to help protect against sunburn.
- Ophthalmologic reactions can occur in patients treated with vemurafenib. Patients should be advised to contact their health care provider immediately for ophthalmologic symptoms.

- Due to potential risk to a fetus woman of child-bearing potential must use effective contraception during treatment with vemurafenib and for 2 weeks after their last dose.
- If a female patient confirms or suspects pregnancy during the study, they should contact their healthcare provider immediately. Any confirmed pregnancy is to be reported within 24 hours as per Section 8.6.
- If a male patient's sexual partner becomes pregnant during the study, they should contact their healthcare provider immediately. Any confirmed pregnancy is to be reported within 24 hours as per Section 8.6.
- Female patients should be advised not to breastfeed during treatment with vemurafenib and for 2 weeks following the final dose.
- Radiation sensitization and recall can occur in patients treated with radiation prior to, during, or after treatment with vemurafenib. Patients should be advised to inform their health care provider if they have had or are planning to receive radiation therapy. Radiotherapy may be allowed while the patient is enrolled in this study if given to help palliate a specific symptom (e.g. bone pain, brain metastases, etc.

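### Section 5.3.1 restarts both drugs after a recovered first Grade 3 or worse reaction, with no express exception for serious hypersensitivity, DRESS, SJS or TEN

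*Combined protocol and SAP*

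**What the plan says.** Section 5.3.1 withholds vemurafenib and sorafenib for any reaction of Grade 3 or worse due to study treatment. It continues: "Upon recovery to Grade 0-1, restart vemurafenib and sorafenib at a reduced dose (dose level -1) as follows". The dose given for a first event is: "Vemurafenib 240 mg twice daily plus sorafenib 200 mg daily for first appearance of Grade 3 or greater adverse reactions". A second such event ends therapy.

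The vemurafenib discontinuation list in the same section has two items. One is a QTc criterion. The other depends on grade: "Grade 4 adverse reaction, first appearance (if clinically appropriate) or second appearance".

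Other sections bear on the same reactions:

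- Section 1.3.1 lists, among the precautions taken from the vemurafenib package insert, "serious hypersensitivity reactions (anaphylaxis and Drug Reaction with Eosinophilia and Systemic Symptoms - DRESS syndrome), Stevens-Johnson syndrome and toxic epidermal necrolysis".
- Section 4.2, item 16, excludes patients with "Known or suspected allergy or hypersensitivity to any of the study drugs (sorafenib, and or vemurafenib) study drug classes".
- Section 9.1, under patient counselling, states: "Anaphylaxis and other serious hypersensitivity reactions can occur during treatment and upon re-initiation of treatment with vemurafenib". It follows with: "Patients should be advised to stop taking vemurafenib and to seek immediate medical attention for symptoms of anaphylaxis and hypersensitivity". For severe skin reactions it says: "Patients should be advised to stop taking vemurafenib and to contact their health-care provider for severe dermatologic reactions".
- Section 5.3 says dose changes follow the dose-modification subsections and also the prescribing information, which is given by link. It adds that if either drug is discontinued for toxicity, both stop.
- Sections 5.6 and 5.8 remove a patient for unacceptable adverse events. Section 6.6 lists toxicity that makes continuing unsafe as a reason to discontinue.

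**The concern.** For most toxicities, hold-and-reduce is a sensible rule. For anaphylaxis, other serious hypersensitivity, DRESS, SJS and TEN, the danger lies in re-exposure. Recovery to Grade 0-1 while the drugs are held shows that the episode has resolved; it does not show that giving the drugs again is safe.

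The section an investigator consults for a dosing decision says to restart. The advice to stop is found in counselling text and in general clauses that first need a judgement. Two investigators facing the same recovered Grade 3 hypersensitivity reaction could therefore act in opposite ways, each pointing to a part of the protocol. At stake is a patient re-exposed to a drug that has already caused a potentially life-threatening reaction.

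**Working it through.** The plan gives no figure on this point and no probability calculation applies. The check is a comparison of provisions, applied to one case: a patient has a first Grade 3 hypersensitivity reaction attributed to study treatment and recovers to Grade 1 within 28 days.

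**Does the restart sentence reach this case?** Yes. The hold is triggered by grade and attribution only, and the restart by recovery to Grade 0-1. Neither sentence sets aside any type of reaction. The verb is directive, not permissive.

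**Does the reduced dose change the picture?** Daily vemurafenib falls from 2 × 480 = 960 mg to 2 × 240 = 480 mg. Daily sorafenib falls from 2 × 200 = 400 mg to 200 mg. Each is halved. The re-initiation warning in Section 9.1 is not limited to full dose, and nothing in the protocol says that half the dose makes re-exposure safe.

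**Does an item in the discontinuation list apply?** Two items, grade-based and QTc; 0 of 2 name any of these reactions. The grade-based item covers a Grade 4 reaction of any type, but at first appearance only where the investigator thinks stopping appropriate. It does not reach Grade 3.

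**Does Table 3 apply?** Table 3 governs sorafenib. It names none of these reactions, and its dermatological rows describe toxicity of the hands and feet. It does show that the protocol uses event-specific bars: permanent discontinuation without resumption is written for gastrointestinal perforation, cardiac ischemia, hemorrhage needing intervention and severe drug-induced liver injury.

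**Does another provision stop the restart?**

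| Provision | What it does | Bars restart in its own words? |
|---|---|---|
| 4.2, item 16 | Excludes known or suspected hypersensitivity at entry | No; entry only |
| 5.3, prescribing information | Has dose changes follow the labels as well | Cannot be judged; label text not reproduced |
| 5.3, both-drugs rule | Stops the second drug once the first is to be discontinued | No; needs a prior decision to discontinue |
| 5.6 and 5.8 | Removes the patient for unacceptable events | No; the event must first be judged unacceptable |
| 6.6 | Allows stopping for unsafe toxicity | No; judgement |
| 9.1 | Has the patient told to stop and seek care | No; silent on permanence and restart |

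None of these is stated to override the restart sentence. The re-initiation warning in Section 9.1 covers anaphylaxis and other serious hypersensitivity; the protocol does not say the same of severe skin reactions.

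**Which cases are exposed?** Two:

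1. A first Grade 3 event that recovers to Grade 0-1 within 28 days, or later in a responding patient if the Principal Investigator confirms.
2. A first Grade 4 event that recovers, where discontinuation is not judged clinically appropriate.

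The two Grade 3 rashes reported in Section 1.4 among the first 3 patients are not described as any of these reactions and are not counted.

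**The case against.** The strongest answer is that Section 5.3.1 is not the whole rule. Section 5.3 makes dose changes follow the prescribing information too, and Section 1.3.1 takes these very reactions from the package insert. If the label bars rechallenge, the protocol already does so by reference, and all that is missing is a repetition. An investigator who restarted would also have to answer the re-initiation warning in Section 9.1 and the mandatory removal in Section 5.8 once an event is judged unacceptable. Serious events are reported within 24 hours or one business day (Section 8.11) and reviewed by an independent committee (Section 12.10.1). The exposed case is narrow, no such event is described in the documents, and no endpoint or error rate depends on it.

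Much of this stands as a limit on the size of the point. Rechallenge is not compelled, and whether the labels close the gap cannot be settled from the documents. It does not remove the point. Section 5.3 gives no order of precedence if its own text and a label differ. The removal clauses take effect only after a judgement that the restart sentence does not prompt. Safety reporting and committee review are not conditions for restarting. If the labels do bar rechallenge, an added line merely puts that rule where dosing is decided.

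A second objection concerns the remedy. Seriousness (Section 8.2.1) and grade (Section 8.4.4) are separate concepts in the protocol, and a possible relationship counts as related (Section 8.4.1), so a broad bullet could stop treatment for a doubtful event. The first part is met by stating that serious means Grade 3 or worse for this rule. The second is a real but small cost. Telling an ordinary Grade 3 rash from a hypersensitivity reaction remains a clinical diagnosis.

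**Conclusion.** The concern holds. Read literally, Section 5.3.1 directs re-exposure to both drugs after a recovered first Grade 3 reaction of a kind for which the protocol itself recognises a danger on re-exposure (serious hypersensitivity) or advises the patient to stop vemurafenib (severe skin reactions). No other wording in the protocol expressly prevents it.

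The size is limited. The gap is one of express wording in two narrow situations. No event rate or patient count is claimed, and the design's error rates and sample size are untouched. No conflict with the drug labels is alleged, because their content is not in the documents. Given the possible harm and the low cost of a remedy, the change should be made at the next amendment. Confidence is medium, mainly because the labels could not be read.

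**What to change.** Add one bullet to the discontinuation list in Section 5.3.1, for example:

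*Anaphylaxis or other serious (Grade 3 or greater) hypersensitivity reaction, DRESS, Stevens-Johnson syndrome or toxic epidermal necrolysis attributed to either study drug: permanently discontinue both drugs at first appearance, with no rechallenge. This overrides the restart instruction in this section and the exception in Section 5.3 for re-initiation after more than 28 days.*

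State that Grade 3 rash or hand-foot reaction not diagnosed as one of these stays under the existing hold-and-reduce rule. A matching row in Table 3 is optional.

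The change needs no extra visits or samples. Its cost is that an occasional patient stops earlier, and a patient who stops before the scan after at least 2 cycles may not be evaluable. Section 5.9 provides for replacement only to reach 7 evaluable patients, not 12, so a loss after the first stage is not expressly covered; the same amendment could settle that.
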